15.4. VITAL SIGNS

The following vital signs measurements will be reported for this study: height [cm], body weight [kg], BMI [kg/m²], body temperature[°C], heart rate [beats/min], respiratory rate [breaths/min], systolic blood pressure [mmHg], diastolic blood pressure [mmHg].

The following summaries will be provided for vital sign data:

- Actual values and change from baseline for vital signs parameter values will be summarized using descriptive statistics at each protocol specified time point by treatment group.
- All vital signs data will be presented in data listings.

DERIVATIONS

- $BMI (kg/m^2) = \text{Body weight (kg)} / \text{Height (m)}^2$

15.5. PHYSICAL EXAMINATION

Physical examination will include examination of general appearance, skin, head, neck (including thyroid), ears, eyes, nose, throat, heart, lungs, abdomen, lymph nodes, extremities and nervous system will be evaluated by the Investigator as Normal, Abnormal NCS or Abnormal CS. New abnormalities occurring after IP administration will be recorded as AEs. Full physical exam will be given at screening and symptom directed physical examination will be given thereafter.

The Investigator's assessment of the physical examination for the various body systems will be listed.

16. DATA NOT SUMMARISED OR PRESENTED

The other variables and/or domains not summarized or presented are:

- Comments
- Skin Biopsy.

These domains and/or variables will not be summarized or presented, but will be available in the clinical study database, SDTM and/or ADaM datasets and listed.

Document: \$506df00529e1\$BDE32479744D47F0B3BAA4285D5BE091.docx

Author: ████████████████████

Version Number: Final v1.1

Version Date: 16Nov2022

Template No.: CS_TP_BS016 Revision 6

Reference: CS_WI_BS005

Effective Date: 02Dec2019

APPENDIX 1. PROGRAMMING CONVENTIONS FOR OUTPUTS

OUTPUT CONVENTIONS

Outputs will be presented according to the following IQVIA Global Biostatistics Standard Output Conventions.

DATES & TIMES

Depending on data available, dates and times will take the format DDMMYYYY; times will take the format HH:MM; combined dates and times will take the format DDMMYYYY/HH:MM. Time will be based on a 24 hour clock.

SPELLING FORMAT

British (UK), except for MedDRA where British English is used.

PRESENTATION OF TREATMENT GROUPS

Only the treatment groups that were actually dosed will be presented in the tables, listings and figures. Study groups that are planned in the protocol but were not conducted will not be included in the outputs.

For outputs, treatment groups will be represented as follows and in that order:

Treatment Group	For Tables and Graphs	For Listings
Placebo	Placebo	Placebo
FT011 200 mg QD	FT011 200 mg	FT011 200 mg
FT011 400 mg QD	FT011 400 mg	FT011 400 mg
Pooled FT011	Pooled FT011	NA
All Participants	All Participants	NA

Document: \$506df00529e1\$BDE32479744D47F0B3BAA4285D5BE091.docx

Author: [REDACTED]

Version Number: Final v1.1

Version Date: 16Nov2022

Template No.: CS_TP_BS016 Revision 6

Reference: CS_WI_BS005

Effective Date: 02Dec2019

Copyright © 2009, 2010, 2012, 2016, 2018, 2019 IQVIA. All rights reserved. The contents of this document are confidential and proprietary to IQVIA Holdings Inc. and its subsidiaries. Unauthorized use, disclosure or reproduction is strictly prohibited.

LISTINGS

The listings will contain data from all scheduled and unscheduled visits, as per the schedule of events Section 2 of the protocol.

All listings will be ordered by the following (unless otherwise indicated in the template):

- Treatment group
- Participant ID
- Date and time (where applicable).

Document: \$506df00529e1\$BDE32479744D47F0B3BAA4285D5BE091.docx

Author: [REDACTED]

Version Number: Final v1.1

Version Date: 16Nov2022

Template No.: CS_TP_BS016 Revision 6

Reference: CS_WI_BS005

Effective Date: 02Dec2019

Copyright © 2009, 2010, 2012, 2016, 2018, 2019 IQVIA. All rights reserved. The contents of this document are confidential and proprietary to IQVIA Holdings Inc. and its subsidiaries. Unauthorized use, disclosure or reproduction is strictly prohibited.

APPENDIX 2. PARTIAL DATE CONVENTIONS

Imputed dates will NOT be presented in the listings.

ALGORITHM FOR DEFINITION OF TREATMENT-EMERGENT ADVERSE EVENTS:

START DATE	STOP DATE	ACTION
Known	Known/Partial/ Missing	If start date < study med start date, then not TEAE If start date >= study med start date, then TEAE
Partial, but known components show that it cannot be on or after study med start date	Known/Partial/ Missing	Not TEAE
Partial, could be on or after study med start date OR Missing	Known	If stop date < study med start date, then not TEAE If stop date >= study med start date, then TEAE
	Partial	Impute stop date as latest possible date (i.e. last day of month if day unknown or 31st December if day and month are unknown), then: If stop date < study med start date, then not TEAE If stop date >= study med start date, then TEAE
	Missing	Assumed TEAE

Document: \$506df00529e1\$BDE32479744D47F0B3BAA4285D5BE091.docx

Author: ██████████

Version Number: Final v1.1

Version Date: 16Nov2022

Template No.: CS_TP_BS016 Revision 6

Reference: CS_WI_BS005

Effective Date: 02Dec2019

Copyright © 2009, 2010, 2012, 2016, 2018, 2019 IQVIA. All rights reserved. The contents of this document are confidential and proprietary to IQVIA Holdings Inc. and its subsidiaries. Unauthorized use, disclosure or reproduction is strictly prohibited.

ALGORITHM FOR DEFINITION OF PRIOR / CONCOMITANT MEDICATIONS:

START DATE	STOP DATE	ACTION
Known	Known	If stop date < study med start date, assign as prior If stop date >= study med start date and start date <= end of treatment, assign as concomitant
	Partial	Impute stop date as latest possible date (i.e. last day of month if day unknown or 31st December if day and month are unknown), then: If stop date < study med start date, assign as prior If stop date >= study med start date and start date <= end of treatment, assign as concomitant
	Missing	If stop date is missing could never be assumed a prior medication If start date <= end of treatment, assign as concomitant
Partial	Known	Impute start date as earliest possible date (i.e. first day of month if day unknown or 1st January if day and month are unknown), then: If stop date < study med start date, assign as prior If stop date >= study med start date and start date <= end of treatment, assign as concomitant
	Partial	Impute start date as earliest possible date (i.e. first day of month if day unknown or 1st January if day and month are unknown) and impute stop date as latest possible date (i.e. last day of month if day unknown or 31st December if day and month are unknown), then: If stop date < study med start date, assign as prior If stop date >= study med start date and start date <= end of treatment, assign as concomitant
	Missing	Impute start date as earliest possible date (i.e. first day of month if day unknown or 1st January if day and month are unknown), then: If stop date is missing could never be assumed a prior medication If start date <= end of treatment, assign as concomitant
Missing	Known	If stop date < study med start date, assign as prior If stop date >= study med start date, assign as concomitant
	Partial	Impute stop date as latest possible date (i.e. last day of month if day unknown or 31st December if day and month are unknown), then: If stop date < study med start date, assign as prior If stop date >= study med start date, assign as concomitant
	Missing	Assign as concomitant

Document: \$506df00529e1\$BDE32479744D47F0B3BAA4285D5BE091.docx

Author: [REDACTED]

Version Number: Final v1.1

Version Date: 16Nov2022

Template No.: CS_TP_BS016 Revision 6

Reference: CS_WI_BS005

Effective Date: 02Dec2019

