Confidence intervals will be reported where appropriate. If not mentioned otherwise, all statistical tests will be performed with a type I two-sided error rate of 5%.

Where appropriate, results will be presented graphically. All reported data will be presented in data listing.

The baseline value for each endpoint is defined as the last available, non-missing value obtained prior to the first study medication administration.

The handling of missing data and adjustments for multiplicity will be described in the SAP.

Pharmacokinetic Analyses

All PK analyses will be based on the PK set.

Descriptive statistics by nominal collection time will be presented for the PK concentrations. Concentrations will also be presented graphically on both linear and semi-logarithmic scales.

The PK parameters will be calculated using non-compartmental analysis methods. Full details will be provided in the SAP.

Descriptive statistics will be presented for the PK parameters.

Safety Analyses

All safety analyses will be based on the safety set.

Medical history findings and AEs will be coded by Medical Dictionary for Regulatory Activities (MedDRA) codes and medications the World Health Organisation Drug Dictionary (WHO-DD) Anatomical Therapeutic Chemical (ATC) classification codes.

Treatment-emergent adverse events (TEAEs) are defined as AEs that started or worsen on or after the first study medication administration. The incidence of TEAEs will be summarised by MedDRA terms and treatment group. Drug-related, serious AEs (SAEs) and TEAEs leading to early study withdrawal will also be summarised. Separate summaries will be produced based on severity and relationship to study drug categories.

	
Other safety endpoints including, vital signs, ECGs, safety laboratory results will be analysed descriptively.
 
Efficacy Analyses
 
All efficacy analyses will be based on the mITT set.
 
Descriptive statistics will be presented for all efficacy endpoints and results will be presented graphically where appropriate.
 
Whilst no formal hypothesis testing is planned, exploratory analyses may be performed to assess the treatment effect of FT011 on the efficacy outcomes. Full details of any inferential analyses will be provided in the SAP.

--	---

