### **10.3 Eliciting and Recording of Adverse Events**

At every study visit, participants must be asked a standard, non-directed question, such as, “How have you been feeling since your last visit?” to elicit any medically related changes in their well-being. They may also be asked if they have been hospitalised, had any accidents, used any new medications, or changed concomitant medication regimens (including prescription drugs, over-the-counter medications, vitamins, herbal products, and minerals). Responses must be documented in the source documents.

In addition to patient observations, AEs must be documented for any clinically significant diagnosis resulting from abnormal laboratory test values, physical examination findings, or ECG abnormalities, or from other documents that are relevant to participant safety.

AEs will be captured from the time of first IMP dose, until the final study visit. Conditions occurring prior to the first dose of IMP will be recorded as medical history. SAEs judged to be possibly related to FT011 occurring to a study participant after the SAE reporting period will be reported to the sponsor if the Investigator becomes aware of them.

It is preferable that AEs are reported as diagnoses if one can be made, rather than individual signs and symptoms. The AE description, start and stop dates, intensity, causality, and outcome must be recorded, as well as any actions taken.

Unless a diagnosis is made, or signs and symptoms are present, abnormal laboratory values, physical examination findings, abnormal vital signs, or ECG abnormalities, should only be reported as AEs if they cause the participant to discontinue from the trial, the investigator feels it is clinically significant, or they meet a criterion for a SAE.

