15.1. ADVERSE EVENTS

AEs will be coded to system organ class (SOC) and preferred term (PT) using MedDRA central coding dictionary, Version 23.0 (or higher).

Treatment-emergent adverse events (TEAEs) are defined as AEs which commence or worsen on or after the date and time of first study drug administration. AEs without an onset date and time will be defined as treatment-emergent except if an incomplete date (e.g., month and year) clearly indicates that the event started prior to start of first study drug administration or if the AE stop date indicates that the event started and/or stopped prior to start of first study drug administration.

All Adverse Events (AEs) summaries will be restricted to the TEAEs only. The number and percentage of TEAEs, Serious TEAEs, TEAEs leading to discontinuation of study treatment and study, and TEAEs related to study treatment will be summarized by SOC, PT and treatment group. The number and percentage of TEAEs by maximum severity will also be summarized.

An overall summary of the number and percentage of participants who had events in each of the categories described below will be produced by treatment group and for all participants.

The following AE summaries will be provided:

- Overview of TEAEs, including:
 - o At least one TEAE
 - o At least one study treatment related TEAE
 - o At least one serious TEAE
 - o At least one study treatment related serious TEAE
 - o Any TEAE leading to death
 - o TEAE leading to study discontinuation
 - o TEAE leading to study drug withdrawal
 - o TEAE leading to study drug interruption
 - o At least one TEAE by maximum severity
 - o At least one study treatment related TEAE by maximum severity
- Incidence of TEAEs by SOC and PT
- Incidence of study treatment related TEAEs by SOC and PT

Document: \$506df00529e1\$BDE32479744D47F0B3BAA4285D5BE091.docx

Author: ████████████████████

Version Number:

Final v1.1

Version Date:

16Nov2022

Template No.: CS_TP_BS016 Revision 6

Reference: CS_WI_BS005

Effective Date: 02Dec2019

Copyright © 2009, 2010, 2012, 2016, 2018, 2019 IQVIA. All rights reserved. The contents of this document are confidential and proprietary to IQVIA Holdings Inc. and its subsidiaries. Unauthorized use, disclosure or reproduction is strictly prohibited.

- Incidence of TEAEs by maximum severity
- Incidence of study treatment related TEAEs by maximum severity
- Incidence of serious TEAEs by SOC and PT
- Incidence of study treatment related serious TEAEs by SOC and PT.

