
In the summary tables, AEs will be presented by decreasing frequency of total participants overall within each SOC and then similarly by decreasing frequency of total participants overall within each PT. SOC or PTs with equal frequencies will be sorted alphabetically.

An overall summary of number of participants within each of the categories described in the subsection below, will be provided as specified in the templates.

The overall Listing of adverse events will include TEAEs and Non-TEAEs. All other listings will include TEAEs only.

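### The SAP's algorithm for treatment-emergent events has no branch for worsening, so it contradicts the SAP's own definition for any AE dated before first dose

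*SAP*

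**What the plan says.** SAP 15.1 gives the definition in words: "Treatment-emergent adverse events (TEAEs) are defined as AEs which commence or worsen on or after the date and time of first study drug administration". The protocol synopsis agrees, counting "AEs that started or worsen on or after the first study medication administration". Protocol 12.4.2.1 is narrower. It mentions only events that commence on or after first dose and says nothing of worsening.

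SAP Appendix 2 gives the algorithm that would be programmed. For a known start date the rule is "If start date < study med start date, then not TEAE", whatever the stop date. A second row, "Partial, but known components show that it cannot be on or after study med start date", leads to the same classification, again whatever the stop date.

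The label decides where an event is reported. SAP 15.1 says: "All Adverse Events (AEs) summaries will be restricted to the TEAEs only". On listings it says: "The overall Listing of adverse events will include TEAEs and Non-TEAEs". All other AE listings are confined to TEAEs.

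On recording, protocol 10.3 captures AEs from first dose and adds: "Conditions occurring prior to the first dose of IMP will be recorded as medical history".

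**The concern.** The definition has two limbs, starting and worsening. The algorithm implements only the first. It should decide the worsening case, and it decides it against the definition.

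The case is a realistic one in this trial. Every participant has diffuse systemic sclerosis at entry, and signs and symptoms of the disease are recorded at Screening and Day 1. Worsening of a condition already present is one way in which harm could appear. The protocol recognises the idea in section 10.2: planned admissions for an existing illness are not AEs, but only if the illness did not deteriorate unexpectedly during the study.

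Treatment-emergent events are a stated secondary safety endpoint. An event wrongly labelled non-TEAE drops out of the incidence tables. It also drops out of the separate listings for drug interruption, drug withdrawal, study discontinuation, death and serious events (SAP 15.1.1.3 to 15.1.1.7). The treatment-emergent tables planned for the DSMB in Appendix 3 rest on the same label.

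**Working it through.** The plan states no figure to reproduce. The check is logical: take an AE that began before first dose and worsened on or after it, and classify it under each rule.

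| Rule | Start date on record | Result |
|---|---|---|
| SAP 15.1 definition | before first dose | TEAE, through worsening |
| Protocol synopsis | before first dose | TEAE, through worsening |
| Protocol 12.4.2.1 | before first dose | not TEAE |
| Appendix 2 | known, before first dose | not TEAE |
| Appendix 2 | partial, must be before first dose | not TEAE |
| Appendix 2 | partial and possibly on or after first dose, or missing | decided by the stop date, never by worsening |

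No row of Appendix 2 tests worsening. Only when the start date is missing or ambiguous can the event come out as a TEAE, and then for a different reason.

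**Can the appendix be confined to incomplete dates?** No. Its title refers to partial dates, but its first row governs fully known start dates, and the table is headed as the algorithm that defines TEAEs.

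**Does precedence settle it?** No. Protocol section 12 puts the SAP above the protocol, which disposes of protocol 12.4.2.1. It cannot resolve a conflict between two parts of the SAP.

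**Does the recording rule settle it?** Only in part.
- If the worsening is entered as a new AE dated at worsening, its start date is on or after first dose. Appendix 2 then classes it as a TEAE, in agreement with SAP 15.1.
- If it is entered with the original onset date, Appendix 2 removes it.
- Protocol 10.3 asks for start and stop dates, intensity, causality, outcome and actions. It does not say which start date a worsening takes, and the fields it lists include no date or flag for worsening.

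**Size per event.** Protocol 12.1 plans 10 participants per group. One participant whose only event is misclassified changes an arm's incidence by 1/10 = 10 percentage points, and the pooled FT011 group's by 1/20 = 5 percentage points. A participant with another event correctly classed as a TEAE still counts in the any-TEAE row, but is lost from the affected preferred-term row and possibly from the severity or seriousness rows.

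**Number of events.** This cannot be derived from the documents. The lower bound is zero.

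**The case against.** The strongest reply is that the gap may never be reached. AEs are captured only from first dose, and the baseline condition already has its own medical history record. The natural reading is then that the AE is the worsening, dated when it happened, and the algorithm classes that correctly. Worsening would also be visible elsewhere: skin score and scleroderma signs at every visit, lung function and global assessments through treatment, laboratory and ECG shift tables, and a separate summary of systemic sclerosis medication. The overall AE listing keeps non-TEAEs, and the DSMB reviews any SAE.

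Much of this stands. It makes the effect conditional and possibly nil. It does not remove the contradiction, because neither document states the recording convention and SAP 15.1 expects non-TEAEs to be present in the AE data.

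A reader might infer three stronger things, none of which the documents support:
- **That the incidence tables will be understated.** This follows only if sites entered original onset dates, and nothing shows that they did.
- **That AE records with a pre-dose start date are mostly worsened conditions.** The expectation of non-TEAEs fits equally well with events entered although they began before dosing.
- **That the algorithm is also wrong to use dates where SAP 15.1 refers to date and time.** That difference would count extra Day 1 events and drop none. SAP 6.5 expressly treats AEs starting on the reference start date as post-baseline, and protocol 10.3 requires only dates. No change is needed there.

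**Conclusion.** The inconsistency is real and lies within the SAP. For an AE with a start date that is known, or clearly shown, to precede first dose and that worsened afterwards, Appendix 2 gives the opposite answer to SAP 15.1 and to the protocol synopsis. Protocol 12.4.2.1 adds a second inconsistency, inside the protocol.

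The consequence is conditional. Where a worsened condition carries its original onset date, it leaves all AE summaries and all TEAE-only listings, at 10 percentage points of arm-level incidence for each participant with no other TEAE. That figure assumes 10 participants per arm, as planned. Where worsening was entered as a new AE dated at worsening, nothing changes. Which of these applies cannot be told from the protocol and SAP.

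The primary pharmacokinetic objective is untouched. The correction is still worth making, because it is cheap and the affected endpoint is the main safety summary of a small trial.

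**What to change.** 1. Add a row to SAP Appendix 2: an AE that starts before first dose, and whose severity or seriousness increased on or after first dose, is a TEAE. Place it ahead of the two rows that now return non-TEAE on a pre-dose start date.
2. Before unblinding, review every AE record with a pre-dose start date against that rule. Alternatively, confirm from the data-entry instructions that worsening was recorded as a new AE dated at worsening, and say so in SAP 15.1.
3. Align protocol 12.4.2.1 with the synopsis and SAP 15.1.

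The cost is one algorithm row, one sentence and a small blinded data review. SAP version 1.1 is dated 16 November 2022, after the completion planned for the third quarter of 2022 in protocol 13.7. If that schedule held, a new CRF flag or site instruction would come too late, so the review in step 2 is the practical route. Because the AE fields listed in protocol 10.3 include no date of worsening, some records may need a judgement from the clinical team. Those judgements should be documented while the team is still blind to treatment.

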#### **6.4 Week 16 (Follow up)**

There is a +1-week window on this visit. At this visit the following will be performed:

- Record any SSc-specific signs and symptoms.
- Investigator assessment of the mRSS (see Section 8.3).
- Symptom-directed physical examination (see Section 8.2).
- Weight.
- Measurement of vital signs including blood pressure, heart rate, respiratory rate, and temperature (see Section 8.2).

- 12-lead ECG (see Section 8.2).
- Safety laboratory tests including haematology, biochemistry, coagulation, and urinalysis, and serum pregnancy test for WOCBP (see Section 8.2).
- Review and record concomitant medications.
- Assess and record adverse events.

This is the final study visit.

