### **7.2 Secondary Endpoints**

#### **7.2.1 Safety Endpoints**

Safety will be assessed by:

- Treatment emergent adverse events from first dose of study drug to End of Study.
- Physical examination.
- Vital signs (blood pressure, heart rate, respiratory rate, and temperature).
- 12-lead ECG.
- Safety laboratory results (haematology, biochemistry, coagulation, and urinalysis).
- Use of concomitant medications.

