#### **12.4.2.6 Prior and Concomitant Medications**

Prior and concomitant medications will be grouped by the WHO-DD ATC classification Level 2 term and by preferred drug name.

Prior medications are those medications that were stopped prior to the first study drug administration. Concomitant medications are medications that are taken at least once after the first study drug administration. Medications stopping on the same day as the first study drug administration will be considered as concomitant medications.

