12. PRIOR AND CONCOMITANT MEDICATIONS

Prior and concomitant medications will be coded using the World Health Organization (WHO) Drug Global Version 01MAR2021 (or later). Prior medications will be recorded up to 1 month prior to baseline observations.

Medications will be grouped by Anatomical Therapeutic Chemical (ATC) system (Level 2) and drug preferred term and summarized by treatment group for the Safety Analysis Set.

- Prior medications are those medications which stopped prior to the first study drug administration.
- Concomitant medications are medications which were taken at least once after the first study drug administration:
 - o started prior to, on or after the first study drug administration AND ended on or after the date of first study drug administration or were ongoing at the end of the study.
 - o Started on or after the date of first study drug administration.

Document: \$506df00529e1\$BDE32479744D47F0B3BAA4285D5BE091.docx

Author: ████████████████████

Version Number:

Final v1.1

Version Date:

16Nov2022

Template No.: CS_TP_BS016 Revision 6

Reference: CS_WI_BS005

Effective Date: 02Dec2019

Copyright © 2009, 2010, 2012, 2016, 2018, 2019 IQVIA. All rights reserved. The contents of this document are confidential and proprietary to IQVIA Holdings Inc. and its subsidiaries. Unauthorized use, disclosure or reproduction is strictly prohibited.

In the listings, each medication will be identified as a prior medication (P), a concomitant medication that started prior to first study drug administration and continued after the first dose of study drug (PC) or a concomitant medication that started after the first dose of study drug ©.

In the summary tables, prior and concomitant medications will be presented by decreasing frequency of total medications overall within each ATC class and then similarly by decreasing frequency of total medications overall within each preferred term. In cases of ATC classes or preferred terms with equal frequencies, medications will be sorted alphabetically.

Systemic Sclerosis Related Concomitant Medications will be summarised separately. Systemic sclerosis (immunosuppressive medications) related concomitant medications will also be summarized separately for participants who have an mRSS increase of 5 or more.

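### SAP Appendix 2 contradicts SAP 12 and Protocol 12.4.2.6 on medications started after end of treatment: a drug with a known start date in follow-up is neither prior nor concomitant

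*SAP*

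**What the plan says.** **Definitions in the body text.** Protocol 12.4.2.6: "Concomitant medications are medications that are taken at least once after the first study drug administration". SAP 12 has the same definition, "Concomitant medications are medications which were taken at least once after the first study drug administration", and its second sub-bullet makes the open end explicit: "Started on or after the date of first study drug administration". In both documents a prior medication is one that stopped before first dose.

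**Algorithm in SAP Appendix 2.** The table crosses start date (known, partial, missing) with stop date (known, partial, missing), giving nine rows.

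- Start known or partial, stop known or partial (four rows): "If stop date >= study med start date and start date <= end of treatment, assign as concomitant".
- Start known or partial, stop missing (two rows): "If stop date is missing could never be assumed a prior medication If start date <= end of treatment, assign as concomitant".
- Start missing, stop known or partial (two rows): "If stop date >= study med start date, assign as concomitant".
- Start and stop both missing (one row): concomitant outright.

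**Collection and purpose.** The Week 16 visit in Protocol 6.4 includes "Review and record concomitant medications". Protocol 7.2.1 names "Use of concomitant medications" as a secondary safety endpoint, and SAP 2.2 repeats it. SAP 12 also plans separate summaries of SSc-related concomitant medications, and of immunosuppressants in participants whose mRSS rises by 5 or more.

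**The concern.** A drug started in follow-up cannot be prior, because it did not stop before first dose. Under the six rows with a limit it is not concomitant either, and Appendix 2 has no third class. Section 12 of the same SAP calls that drug concomitant.

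The limit also works unevenly. The best-documented records, those with an exact start date after end of treatment, are the ones left out, while the same drug with no start date is counted. A wish to report on-treatment use only would not explain that pattern.

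At stake is the completeness of a descriptive safety summary. Treatment-emergent adverse events run to end of study (SAP 2.2), and the TEAE table in the same appendix has no end-of-treatment limit. An adverse event in follow-up could therefore be tabulated while the drug given for it is not. Follow-up starts would be missing from the SSc-related summary in the same way.

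**Working it through.** The plan gives no figure to reproduce. The check applies the rows as written and compares the result with the definitions.

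**Inputs.** Treatment is 12 weeks and follow-up 4 weeks (Protocol 5.3). The Week 16 visit has a window of +1 week (Protocol 6.4). End of treatment is taken as Day 84, which is an assumption because the SAP does not define the term.

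**Step 1: one illustrative drug.** First dose 10 January 2022, so Day 84 is 10 January + 83 days = 3 April 2022. The drug starts on 14 April and stops on 19 April. The stop date is after first dose, so it is never prior.

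| Start date as recorded | Start date used | On or before 3 April? | Appendix 2 | SAP 12 and Protocol 12.4.2.6 |
|---|---|---|---|---|
| 14 April 2022 | 14 April 2022 | No | No class | Concomitant |
| April 2022, day missing | 1 April 2022 | Yes | Concomitant | Concomitant |
| 2022, day and month missing | 1 January 2022 | Yes | Concomitant | Concomitant |
| Missing | None | No limit applies | Concomitant | Concomitant |

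**Step 2: all follow-up starts.** Take a drug started on each of days 1 to 28 after Day 84, for 365 assumed first-dose dates from 1 June 2021: 365 × 28 = 10,220 cases. The result is the same whether the stop date is known, partial or missing.

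- Full start date: 10,220 of 10,220 have no class (100%).
- Day missing: 4,872 of 10,220 have no class (47.7%). The rest are imputed back into the treatment period.
- Day and month missing: 406 of 10,220 have no class (4.0%).
- Start date missing: 0 of 10,220 have no class.

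The two partial-date shares depend on the assumed calendar. The full-date and missing-date results do not.

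**Step 3: uncovered time after first dose.**

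- Planned: 4 / (12 + 4) = 4/16 = 25%.
- With the visit window: 5 / (12 + 5) = 5/17 = 29%.

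**Step 4: effect of removing the limit.** Every follow-up start becomes concomitant, in agreement with SAP 12 and Protocol 12.4.2.6. Drugs started on treatment are classed as before.

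**Step 5: is the limit a declared change?** SAP 3.3 lists two changes from the protocol, the added screened set and the inverted patient global score. The limit is not among them.

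**The case against.** The strongest reply is that nothing need be lost. Appendix 2 is headed as a set of partial-date conventions, and no text says that it overrides Section 12. If Section 12 is programmed, every follow-up start is concomitant. This stands, and it makes the loss conditional. It does not remove the contradiction: the table presents itself as the algorithm defining the two classes, and its row for two known dates carries the limit. The protocol's rule that SAP methodology takes precedence (Protocol 12) does not help, because the conflict lies inside the SAP.

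A second reply is that the data survive. Protocol 5.4.5 requires every medication to be recorded with dates and indication, and SAP Appendix 1 has the listings cover all scheduled and unscheduled visits. This also stands. What is affected is a summary count and the P/PC/C code, not the record.

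A third is that the immunosuppressant summary for an mRSS rise of 5 or more follows a rule stated for the Treatment Period, so follow-up starts may be marginal to it. That is a fair reading, although SAP 12 does not restrict the summary to that period.

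Some stronger inferences are not supported:

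- **That the Week 16 mRSS could not be interpreted, or that efficacy results are affected.** The listings would show new therapy with its dates. The models in SAP 7.1 and 14.2.1.10 use baseline value, treatment, visit and participant terms, not the medication class.
- **That a quarter of medication records would be lost, or that drugs are especially likely to be started once study drug stops.** The documents give no rate of follow-up starts.
- **That every follow-up start is excluded.** Missing start dates and some partial ones are kept.

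**Conclusion.** The contradiction is real and the Appendix 2 rule is wrong as written: it leaves a drug with no class when its start date, after any imputation, falls after end of treatment, although both definitions call that drug concomitant.

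The consequence is confined to descriptive safety output, and it arises only if Appendix 2 is the version programmed. In that case all fully dated follow-up starts are missing from the concomitant-medication summaries, including the SSc-related ones, and have no valid code under the algorithm. The 25% (up to 29%) measures time not covered. The number of drugs affected cannot be derived from the documents. The time figures take Week 12 as end of treatment; for a participant who stops early, they depend on whether the term means last dose or a visit. No estimate, interval or p-value in the efficacy analysis changes, and SAP 15 plans no statistical comparison of safety outcomes.

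**What to change.** In the six Appendix 2 rows with a known or partial start date, delete the end-of-treatment condition, or replace it with a start no later than the final study visit. Either version brings Appendix 2 into line with SAP 12 and Protocol 12.4.2.6. The three missing-start rows can stay as they are.

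If on-treatment use is wanted as a separate summary, define end of treatment (date of last dose, or date of the Week 12 or early termination visit). A flag for drugs started after that date is then optional.

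The cost is a short SAP revision with an entry in its modification history and a small change in derivation code. No new data are needed, since medications are already collected at Week 16.
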